If you are a woman capable of becoming pregnant, we will ask you to have a pregnancy test before beginning this study. You must use effective birth control methods and try not to become pregnant while participating in this study. If you become pregnant, there may be unknown risks to your unborn child, or risks to your unborn child that we did not anticipate. There may be long-term effects of the treatment being studied that could increase the risk of harm to an unborn child. You must tell the doctor if your birth control method fails while you are on the study. If you believe or know you have become pregnant while participating in this research study, please contact the research team member identified at the top of this document as soon as possible. Please discuss with the research team how long you need to wait before becoming pregnant after completing the treatment or procedures on this study.

If you are a sexually active male it is important that your partner not become pregnant during your participation in this study. There may be unknown risks to the unborn child or risks we did not anticipate. You and your partner must agree to use birth control if you want to take part in this study. If you believe or know that your partner has become pregnant during your participation in this study, please contact the research team member identified at the top of this document as soon as possible.

LOCATIONS / SITES OF STUDY

Data collection: Washington University School of Medicine

Data analysis: Washington University School of Medicine

STUDY DURATION

Anticipated duration of entire research activity per patient:

- Aim 2: Three days over the course of 1½ to 3 months*
- Patients not in Aim 2: Two days, which can occur up to a few weeks apart*

* One additional make-up scan day will be allowed for each subject, with his/her consent, in the event of technical problems that prevent completion of the scan day procedures. MRI equipment failure or a broken infusion pump are examples of such technical problems.

Anticipated duration of entire research activity:

Three years

SAMPLE SIZE

Aim 1: N = 20

Aim 2: N = 10 (up to 2 subjects can overlap between groups)

The N's above refer to subjects who are eligible after screening procedures and who continue in the study. Additional subjects may be screened to reach this number of eligible subjects.

Power considerations: For a first study of a method, there is no information available to confidently

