predict variance of the key outcome measures and provide a formal power analysis. We have chosen the sample sizes here pragmatically, to allow recruitment and scanning at a steady, practically achievable rate. We note that the sample size of 20 for Aim 1 provides power >80% to find a moderately strong positive correlation ($r = 0.5$) while maintaining a low false positive rate $\alpha=0.05$. Power exceeds 99% to find a very strong correlation that would explain half the variance in disease severity ($r = 0.7$).

Additional levodopa-naïve subjects would not help Aim 1 substantially, as a Pearson correlation analysis is not appropriate if a large fraction of subjects are lumped at one end of the range of disease duration or severity. Therefore we plan to limit to 2 the number of subjects included in both Aims. However, if severity or duration vary substantially among the never-treated subjects, we may include more than two of them in the Aim 1 analysis. The number of subjects for Aim 2 is largely pragmatic, given the difficulty of recruitment and the additional cost with 2 scans per subject.

INCLUSION CRITERIA

There are two groups of subjects. All have idiopathic Parkinson disease. For the first group, we will attempt to sample a broad range of severity and disease duration. The second group will not be treated currently with levodopa, so most subjects in this group will be early in the disease process.

Inclusion criteria for all subjects:

- Age 40-79 at screening
- Meet accepted diagnostic criteria for Parkinson disease

EXCLUSION CRITERIA

Exclusion criteria for all subjects:

- Pregnancy
- Metal in the head or eye, or other contraindication to MRI
- Deep brain stimulator (DBS)
- Patients taking a dopamine antagonist or dopamine partial agonist
- Claustrophobia
- Significant neurologic disease other than PD (exceptions would include febrile seizures or uncomplicated migraine)
- Head trauma with loss of consciousness for more than 5 minutes
- Severe or unstable systemic illness
- MMSE < 24
- History of a primary psychotic disorder
- Current severe major depressive episode (clinical diagnosis after psychiatric interview)
- Current alcohol use disorder (clinical diagnosis after screening with the Michigan Alcoholism Screening Test)
- Current psychosis
- Subjects who feel that going without nicotine for 3-4 hours would be uncomfortable
- Currently taking an extended-release formulation of a dopamine agonist

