3. Left and right caudate VOIs (LC, RC).
4. Left and right anterior putamen (LaP, RaP) as defined above. The nucleus accumbens is excluded.
5. Left and right nucleus accumbens (LNA, RNA).
6. Thalamus (Th).
7. Each voxel in the brain.

The primary analysis will be a correlation across all Aim 1 subjects of the k_e 's for a VOI to clinical measures of disease severity and duration. Duration of illness will be measured from the first symptom, as recorded on the screening day. Standard 20cm tapping speed in the L and R hand and hemi-UPDRS part III motor scores, both measured in the standard off condition, will capture the increased variance provided by clinical asymmetry and will be correlated with contralateral posterior putamen k_e . Midbrain k_e will be compared to total "off" UPDRS part III scores and tapping speed in the more affected hand. Specifically:

The primary comparisons for Aim 1 will be simple Pearson correlations:

1. between the off-period 20cm tapping speed in the more affected hand and the midbrain k_e , and
2. between the off-period total UPDRS part III motor score and the midbrain k_e .

Secondary comparisons for Aim 2 will be correlations:

3. between "off" 20cm tapping speed on each side and contralateral posterior putamen k_e , and
4. "off" hemi-UPDRS part III motor scores on each side and contralateral posterior putamen k_e .

For #3 and #4, we will calculate the r values using repeated measures correlation [24], with side as the repeated measure, rather than as $2n$ independent data points. However, we are interested in between-subject correlation as well as the within-subject r_{rm} that the `rmcorr` package focuses on, so we will also report that p value (corresponding to the first row in Table 3 of ref. [24]).

For Aim 2, the k_e 's for each VOI will be compared before and after 6 weeks of treatment in a repeated measures ANOVA analysis. Here the key comparison is whether k_e changes with time (before vs after treatment) in any VOI, controlling for side (more affected side vs less affected side). Our hypothesis is that this change with time is at or near 0, so our answer will be framed in terms of 95% confidence intervals for change. Any VOIs identified from the Aim 1 SPM analysis will also be tested.

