- Explain that the purpose is to get them to a dose that causes clear, short-term improvement in PD symptoms during the next few weeks, but that has tolerable side effects (if any).
- Discuss possible benefit by reviewing their current typical PD motor symptoms.
- Discuss common side effects, including non-CNS (nausea, drop in blood pressure upon standing) and CNS (sleepiness, dyskinesias, rarely hallucinations) side effects.
- Give the patient a copy of the “Carbidopa-levodopa for Parkinson’s disease” handout.
- Ask them to keep track of any missed doses and of any observations or questions for us (e.g. on a 3x5 card or on a smart phone note).
- Confirm contact information and schedule a phone call within the next week.
- Give patients your and my contact information and encourage them to call with any concerns about the medication.

Start treatment with CD-LD 25/100mg tablets, one half tablet by mouth b.i.d. (morning and early afternoon).

Questions at each scheduled follow-up contact

- What symptoms are better?
- What symptoms are not?
- If not expressed spontaneously, inquire about each of these: tremor, stiffness, slowness, speech and gait
- If there is any benefit:
 - How long does it take to “kick in”?
 - How long does the benefit last?
- Any side effects?
- If not expressed spontaneously, inquire about the non-CNS and CNS side effects listed above.
- Are you satisfied with your treatment? Do you have any questions for me?
- (After 4 weeks) About how many tablets do you have left? [Enough until Scan Day 2?]

Dosing

1. If there is a CNS side effect other than mild, tolerable sleepiness, or for any questions, discuss with the PI.
2. Proceed based on the category below that best describes the patient’s current situation:
 - a. **Still has bothersome PD symptoms, no or minimal side effects:** If patient has been on current dose for less than 5 days, no change. If patient has been on current dose for at least 5 days, increase dose by one level (see dosing table below).
 - b. **Still has bothersome PD symptoms but also has non-CNS side effects:** If mild side effects and taking less than 100mg carbidopa per day, increase dose by one level. Otherwise add carbidopa 50mg p.o. q a.m., ½ hour before first CD-LD dose.

- c. **Still has bothersome PD symptoms but also has CNS side effects:** If patient had clear benefit at the previous dose, return to previous dose. Otherwise consult with PI.

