- d. **Clear improvement and no remaining bothersome PD symptoms:** Continue drug at current dose schedule.

Dosing table for CD-LD 25-100mg tablets p.o.		
Level	Dose schedule	Total daily dose LD (mg)
1	0.5 tablets b.i.d.	100
2	0.5 tablets t.i.d. (morning, approximately noon, approximately 5pm)	150
3	
 ▪ if patient has had NO wearing off between b.i.d. doses: 1 tablet b.i.d.; ▪ if patient has had wearing off between b.i.d. doses: 1 tablet q a.m. plus 0.5 tablet at noon and at 5pm 	200
4	1 tablet t.i.d.	300
5	1.5 tablets t.i.d.	450
6	2 tablets t.i.d.	600
7	2.5 tablets t.i.d.	750

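### Aim 2 expects no change in k_e, but its analysis ignores whether treatment was taken, so non-adherence pulls the estimate toward the expected answer

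*Combined protocol and SAP*

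**What the plan says.** All places are in the combined protocol and SAP.

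- **Data analysis, Aim 2 paragraph.** The k_e values "will be compared before and after 6 weeks of treatment in a repeated measures ANOVA analysis". The key comparison is time (before or after treatment), controlling for side. The plan then states its expectation: "Our hypothesis is that this change with time is at or near 0". On how the result will be reported, it adds: "so our answer will be framed in terms of 95% confidence intervals for change".
- **Sample size.** "Aim 2: N = 10 (up to 2 subjects can overlap between groups"; "The number of subjects for Aim 2 is largely pragmatic". On variance: "For a first study of a method, there is no information available to confidently" predict it.
- **Treatments and Dosage, and the dosing appendix.** Oral carbidopa-levodopa (CD-LD) is individualised to benefit and side effects. The dosing table runs from 100 mg levodopa a day at level 1 to 750 mg a day at level 7 ("2.5 tablets t.i.d").
- **Dosing appendix, initiation of treatment.** Staff are told: "Ask them to keep track of any missed doses and of any observations or questions for us", for example on a card or a phone. The listed questions for follow-up contacts do not include missed doses. A question on tablets left, asked after 4 weeks, checks supply up to the second scan.
- **Additional analysis details.** The stated exclusions are a missing k_e or a missing off-state score. Interactions are planned with demographic or disease variables, with age and dyskinesias as examples. Oral dose and adherence are not named.

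**The concern.** When a study looks for a difference, analysing everyone regardless of adherence is the cautious choice. When the expected answer is no difference, it is the lenient one. Aim 2 is of the second kind: it is meant to show that ordinary treatment does not disturb k_e, which matters if k_e is to serve as a progression marker in treated patients.

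The planned time factor has two levels, before and after. A subject who was rescanned but had stopped CD-LD, or had missed many doses, contributes an after value that carries little or no treatment effect. If treatment does change k_e, such subjects shrink the estimated change. Reporting an interval does not remove this, because the interval is centred on the shrunken mean. With ten subjects, each one carries a tenth of the result.

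**Working it through.** **Plan's own figure.** None exists for Aim 2. The documents give no power, SD of change, effect size, adherence rate or margin for near zero, so what follows is an illustration.

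**Inputs.** From the documents: n = 10 and a 95% interval. Assumed: one change score per subject, normal with SD 1 (so effects are in SDs of change); a true change δ = 1 in subjects who took treatment; k subjects with either no effect or half the effect.

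**Step 1: precision.** Half-width = t(0.975, n − 1)/√n.
- n = 10: 2.262/√10 = 0.715 SD
- n = 9: 2.306/√9 = 0.769 SD
- n = 8: 2.365/√8 = 0.836 SD

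**Step 2: shift of the mean.** If k of 10 have no effect, the expected mean is (1 − k/10)δ, which is 0.9 for k = 1 and 0.8 for k = 2. If they have half the effect, it is (1 − 0.5k/10)δ, which is 0.95 and 0.90. The direction is toward zero for any δ.

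**Step 3: how often the interval includes 0.** Simulated one-sample t intervals, at least 200,000 trials per case. The on-treatment set leaves out the k subjects.

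| Case | All 10 subjects | On-treatment set alone | Both sets |
|---|---|---|---|
| k = 0 | 20% | – | – |
| k = 1, no effect | 32% | 25% | 22% |
| k = 2, no effect | 45% | 32% | 27% |
| k = 1, half effect | 25% | 25% | 20% |
| k = 2, half effect | 30% | 32% | 23% |

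**Step 4: does the interval rule out the true effect?** With one or two wholly unexposed subjects, the all-subjects interval still contains the full 1 SD change in 95% or 93% of trials. It both includes 0 and excludes 1 SD in 3% or 5%, against 2% with none unexposed.

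**Step 5: sensitivity to δ.** With two wholly unexposed subjects, the interval includes 0 in 81% of trials for δ = 0.5 (71% with none) and in 31% for δ = 1.2 (8% with none).

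**The case against.** The strongest reply is that Aim 2 asks about clinically dosed treatment, meant to match routine practice, and that the plan reports an interval without any rule that an interval including 0 proves no effect. Several parts of this stand.

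- **Dose range.** A reader might infer that the permitted spread of final daily dose, 750/100 = 7.5-fold, is itself an exposure defect. The documents do not support that. Dose is titrated to response, and a subject with clear improvement and no bothersome symptoms stays at the current level by design. Such a subject on a low dose is treated as the aim defines it.
- **Everyone counted as fully treated.** This too might be inferred, but the plan never says it. It follows only from silence and from the two-level time factor. The plan also does not say that subjects who stopped early will be rescanned.
- **One or two poor adherers can produce a false conclusion.** Step 4 limits this: the interval seldom excludes the true effect.
- **Partial exposure.** Missing some doses is not zero exposure. At half effect, dropping those subjects brings no gain by itself (25% and 32%, against 25% and 30%). The gain comes from requiring both sets to agree.
- **Data.** Missed-dose notes are informal and no listed follow-up question collects them, so the remedy needs a little more than SAP wording.

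What does not stand is any suggestion that the plan already handles adherence. The open-ended interaction statement does not name it, and no analysis set depends on it.

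**Conclusion.** The point holds in a limited form. Aim 2 expects no change, its analysis uses no adherence information, and subjects who did not take treatment would move the estimate toward the expected answer. That direction is certain if treatment truly changes k_e; if it does not, there is no harm, but the plan as written could not tell the two situations apart.

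The size is illustrative and rests on the assumed 1 SD change and the assumed number and type of unexposed subjects. Under those assumptions, one or two wholly unexposed subjects raise the share of intervals that include 0 from 20% to 32% or 45%. Requiring an on-treatment set to agree lowers this to 22% or 27%. At half effect, 25% or 30% falls to 20% or 23%. The problem is therefore a lenient reading of no change, and the remedy is a cheap improvement to a small first study of a method. It does not supply a margin for near zero, which the plan also lacks.

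**What to change.** 1. Report the 95% interval for change in two sets defined in advance: all rescanned subjects, and an on-treatment set of those still taking CD-LD up to the second scan who meet an adherence threshold fixed before the data are examined. The threshold is for the study team to set.
2. Claim no effect of treatment only if both intervals support it.
3. Add a missed-dose question to the follow-up contacts already scheduled, drawing on the notes patients are already asked to keep.
4. If k_e change is plotted against cumulative dose, or the SD of individual changes is reported, label both as descriptive. Dose rises with persisting symptoms and so is confounded with severity. Without an untreated test-retest scan, the SD mixes measurement error with real differences in response.

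**Cost.** A paragraph in the analysis plan and one extra question per contact. No dose or treatment rule changes. The on-treatment set is smaller, so its interval is wider: 0.84 SD half-width at n = 8, against 0.72 SD at n = 10.

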Figure 1. Across groups of PD patients, k_e is a surrogate for disease duration

[figure not shown]

Figure 2. Patients from different Hoehn and Yahr stages of PD are predicted to show different time courses of brain activity (unpublished data).

accurate k_e for a brain region that responds to exogenous levodopa with a dose-response curve anywhere close to that of clinical response. Midbrain, for instance, has a robust rCBF response to single, clinically sensible doses of levodopa [9-12,14].

This study's goal is to validate "bucket mapping" as an objective, quantitative measure of disease severity in PD. Success would position the new method for use as a surrogate endpoint in clinical studies of putative disease-modifying therapies for PD, potentially speeding up such trials dramatically.

Specific Aims

1. Test whether dopamine buffering capacity in midbrain and posterior putamen, measured by levodopa pHMRI, reflects clinical disease severity (disease duration, off-period motor function and clinical asymmetry) in 20 PD patients covering a range of current symptom severity and disease duration.
2. Test whether regional k_e values are affected by clinical treatment (6 weeks of clinically dosed carbidopa-levodopa (CD-LD) in 10 previously untreated PD patients).

Secondary Hypothesis

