In Parkinson's disease (PD), while motor disturbances are the predominant and most readily recognized symptoms, various non-motor symptoms frequently co-occur. Cognitive functions such as working memory and executive control are on average worse in PD, although with substantial variability across patients. This variability highlights the need for ongoing studies exploring the nature of cognitive deficits in PD and their relationship to disease severity and progression. This study utilizes pHMRI-measured dopamine buffering capacity in putative motor regions as a model of motor disease severity. We propose extending this approach to include measures of cognitive performance utilizing [the NIH Toolbox](#) [22]. The NIH Toolbox cognitive measures were chosen because they can be completed relatively quickly (important to minimize patient discomfort when assessed in the medication off state), because it incorporates tasks that directly assess functions known to be impaired in PD, and because of its recognized validity [23]. The hypothesis is that the extent of DA buffering capacity loss in pertinent regions (such as the caudate nucleus) will explain a significant fraction of the variance in specific cognitive abilities.

Secondary Aim

3. Test whether dopamine buffering capacity in caudate reflects severity of cognitive dysfunction.

STUDY DESIGN

Overall study timeline

The study is planned for complete enrollment within 3 years.

Overview of each subject's participation

After thorough clinical assessment on a screening visit, subjects return on a separate day for levodopa pHMRI. Clinical severity ratings are repeated. Regional CBF data from pre-specified brain VOIs (volumes of interest) are collected continually with ASL fMRI before levodopa, during a 10-minute i.v. loading dose, and then repeatedly over the next approximately 90 minutes.

Levodopa-naïve patients in Aim 2 will have all scan day procedures repeated identically on a second scan day after 6 ± 1 weeks of clinically dosed treatment with CD-LD.

Screening visit

1. Potential subjects will review a written informed consent document with the investigator or designee and will have opportunity to resolve questions or concerns. All procedures below are performed only after written documentation of consent.
2. We will collect the following measures at screening:
 - a. Basic demographic information
 - b. MRI safety checklist
 - c. Handedness (Edinburgh Handedness Inventory)

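### Does Aim 2 need a stated size for a k_e change that counts as near zero?

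*Combined protocol and SAP*

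**What the plan says.** The Data analysis part of the analysis plan says that the k_e values "for each VOI will be compared before and after 6 weeks of treatment in a repeated measures ANOVA analysis". It continues: "Here the key comparison is whether k_e changes with time (before vs after treatment) in any VOI, controlling for side", with side meaning the more against the less affected side. It then gives the expectation, "Our hypothesis is that this change with time is at or near 0", and the form of the result: "our answer will be framed in terms of 95% confidence intervals for change". It adds: "Any VOIs identified from the Aim 1 SPM analysis will also be tested".

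The Sample Size section sets N = 10 for Aim 2, largely on pragmatic grounds. It says that, for a first study of the method, there is no information with which to "predict variance of the key outcome measures and provide a formal power analysis". Its correlations of r = 0.5 and r = 0.7 illustrate power for Aim 1 with 20 subjects. No expected precision is given for Aim 2.

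The Objectives section gives the long-term purpose: "Success would position the new method for use as a surrogate endpoint in clinical studies of putative disease-modifying therapies".

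**The concern.** A hypothesis of little or no change can be supported only against some idea of how much change is little. The plan names none. With 10 paired observations, an interval that contains zero may also contain a shift large enough to matter. The same wide interval could then be described afterwards either as showing a change near zero or as unresolved.

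The stake is the surrogate role. If symptomatic treatment itself moves k_e by an amount comparable with the differences that k_e is meant to show between milder and more severe disease, k_e would be hard to interpret in a trial of a disease-modifying drug. Aim 2 is the part of the study that addresses this, so a loose reading of its result would be costly.

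Three smaller gaps looked related. The plan does not say how the primary and secondary ranking of regions applies to Aim 2, it does not say outright that there is one model per region, and a side factor cannot apply to midbrain or thalamus, which are not split into left and right.

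**Working it through.** The plan gives no power, margin or interval width for Aim 2, so there is no figure to reproduce. The check asks how wide the intervals would be, and then whether the plan draws a conclusion that this width cannot support.

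**Inputs.** From the documents: N = 10 and 95% intervals. Assumed, because the documents do not give them:
- scan-rescan reliability ρ of 0.5, 0.75 or 0.9;
- equal SDs at both scans and in the two groups, and no variation between patients in the treatment effect;
- a benchmark shift of 0.5 between-subject SD of k_e. At r = 0.5, this is the k_e difference that goes with 1 SD of severity. The plan uses r = 0.5 only to illustrate power, so this is a yardstick and not the sponsor's expected effect.

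**Half-width, one k_e per scan (midbrain, thalamus).** t(0.975, 9)/√10 = 2.262/3.162 = 0.715 SD of the within-subject change.

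**In between-subject SDs.** SD of change = √(2(1 − ρ)) × SD of k_e.

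| ρ | SD of change | Half-width | P(interval contains 0, true shift 0.5 SD) |
|---|---|---|---|
| 0.5 | 1.000 | 0.72 | 71% |
| 0.75 | 0.707 | 0.51 | 49% |
| 0.9 | 0.447 | 0.32 | 12% |

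The last column uses a noncentral t with 9 degrees of freedom and noncentrality √10 × 0.5/(SD of change): 1.58, 2.24 and 3.54. An interval centred on zero excludes a 0.5 SD shift only if ρ exceeds 1 − (0.5/0.715)²/2, about 0.76.

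**Two-sided regions.** Posterior putamen, caudate, anterior putamen and accumbens are listed left and right, so the time effect averages two values. With error correlation c between sides, the SD of change is multiplied by √((1 + c)/2). At ρ = 0.75 per side:
- c = 0.5: 0.707 × 0.866 = 0.612, half-width 0.44, interval contains 0 in 37% of trials;
- c = 0: 0.707 × 0.707 = 0.500, half-width 0.36, interval contains 0 in 20%.

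The plan notes that pharmacokinetic error is shared by all regions within a subject, so c = 0 is unlikely. The size of the gain is unknown.

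**What the plan does with the interval.** The percentages above describe a rule that reads an interval containing zero as no change. The plan has no such rule. It sets up no equivalence test and promises no verdict; it reports the interval. At ρ = 0.5 a reader would see limits near ±0.72 SD and know that a 0.5 SD shift had not been excluded.

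**The smaller gaps.** The wording of the comparison already points to a separate analysis for each region. The primary and secondary list stands in the general Data analysis text and is not confined to Aim 1. Any analyst will leave the side factor out for a region that has no sides.

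**The case for a change.** The strongest case for a change is that an interval supports a claim of little change only against a benchmark, and that the benchmark is worth most when fixed before the data are seen. Unknown variance does not prevent this: a margin could be written as a fraction of the between-subject SD of k_e in Aim 1, so no forecast is needed. The cost is a line of text.

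Part of this stands. No size is stated, the arithmetic is right, and at moderate reliability an interval from 10 patients will often be too wide to settle the surrogate question.

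The rest is weaker. The proposed scale is debatable: Aim 1 deliberately samples a broad range of severity and duration, whereas Aim 2 patients are expected to be mostly early in the disease. A margin tied to the Aim 1 SD would therefore depend on how wide the recruitment turned out to be, and that SD also contains measurement error. From 20 subjects it is itself uncertain, with a 95% interval of 0.76 to 1.46 times the estimate (√(19/32.85) to √(19/8.91)). With a margin of 0.5 SD, reliability 0.75 and no true change, a region with one k_e per scan would read as near zero in only 17% of trials. The label in the other 83% would almost always be inconclusive, which the width of the interval already tells the reader.

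**Conclusion.** No change is needed. The missing margin is a gap in detail. Carried out exactly as written, Aim 2 yields valid 95% intervals for change, and their width discloses any lack of precision. For a first study of a method, with variance unknown and N set pragmatically, estimation without a formal equivalence margin is a fair choice.

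The firm figure is the half-width of 0.72 SD of within-subject change for a region with one k_e per scan; it rests on N = 10 and normally distributed changes. Everything expressed in between-subject SDs depends on a reliability that the documents do not give. The chance that an interval misses a 0.5 SD shift runs from 12% to 71% over the range tried, and is lower where two sides are averaged. Those figures cannot carry a claim that Aim 2 will fail to detect a shift of disease-related size.

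If the sponsor wishes, one sentence written before the Aim 2 k_e values are seen could say what size of change would matter for surrogate use, and that an interval containing both zero and that size is inconclusive. This would help readers but would not alter the analysis. A careful report would describe such an interval in that way in any case.
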